5.4.2. Additional considerations

All analyses will be descriptive and will be based on the Exposed Set (ES).

Compliance in completing solicited adverse events information will be tabulated after each dose and overall.

The percentage of subjects with at least **one local solicited** AE, with at least **one general solicited** AE and with **any solicited** AE during the 7-day follow-up period will be tabulated with exact 95% confidence interval (CI) after each dose and overall. The same computations will be done for Grade 3 AEs, for any AEs considered related to vaccination, and for Grade 3 AEs considered related to vaccination.

The number of days with solicited symptoms reported during the **7-day follow-up period** will be tabulated for each solicited adverse event, after each dose using descriptive statistics (mean, min, Q1, median, Q3, maximum).

The same tabulation will be done for Grade 3 symptoms, and also during **the whole post-vaccination period** (to include the total number of days for symptoms ongoing beyond the follow-up period).

The incidence of each solicited symptom (any grade and grade 3) will also be represented graphically per group and per dose.

Analysis of solicited symptoms will also be done:

- on the **pooled groups according to adjuvant content** (AS01B, AS01E, Plain), overall and by age category.
- On symptoms reported during the 4-day period, i.e. on the day of vaccination and 3 subsequent days, for each group after each dose and overall.

CONFIDENTIAL

208851 (RSV OA=ADJ-002)
 Statistical Analysis Plan Amendment 2

5.4.2.1. Solicited Adverse Events

Solicited adverse events will be reported daily during the 7-day (from Day 1 to Day 7) follow up period after each vaccination, using structured diaries. Missing or non-evaluable measurements will not be replaced.

In order to summarize the data, the maximum intensity of local injection site redness/swelling (in mm) and fever (in °C) will be categorized as follows:

Grading	Redness/swelling	Fever
0:	≤ 20 mm	< 38.0°C (100.4°F)
1:	> 20 - ≤ 50 mm	≥ 38.0°C (100.4°F) - ≤ 38.5°C (101.3°F)
2:	> 50 - ≤ 100 mm	> 38.5°C (101.3°F) - ≤ 39.0°C (102.2°F)
3:	> 100 mm	> 39.0°C (102.2°F)

Fever is defined as temperature $\geq 38.0^{\circ}\text{C} / 100.4^{\circ}\text{F}$ (regardless of the location of measurement). The preferred location for measuring temperature in this study will be the oral cavity. Body temperature will also be summarized by 0.5°C increments as follows: $\geq 38.0, > 38.5, > 39.0, > 39.5, > 40.0^{\circ}\text{C}$.

Each subject's data will be summarized according to the maximal severity observed during the follow-up period for each adverse event and each dose, followed by a summary across subjects and across doses.

5.4.2.2. Unsolicited Adverse Events

When an unsolicited adverse event occurs more than once for a subject, the maximal severity and strongest relationship to the vaccine group will be counted. The selection of unsolicited AEs reported during the follow-up period will be done using the day of onset.

The analysis of unsolicited adverse events includes the following categories:

- Any unsolicited adverse event.
- Possibly related unsolicited adverse events.
- Grade 3 unsolicited adverse events
- Grade 3 possibly related unsolicited adverse events.
- Serious adverse events (SAEs)
- Possibly related SAEs.
- Potential Immune-Mediated disease (pIMDs, in Part B only)
- Medically attended adverse events

SAEs and pIMDs reported during the entire study period will be tabulated.

CONFIDENTIAL

208851 (RSV OA=ADJ-002)
 Statistical Analysis Plan Amendment 2

In addition, the following time periods will be considered to report SAEs/pIMDs at the first and second analyses (E1_02 and E1_03, see section 7.1):

- from Dose 1 up to 30 days post dose 2 (or up to 90 days post dose 1 for subjects who did not receive the second dose)
- from Dose 1 up to 6 months* post dose 2 (or up to 8 months* post dose 1 for subjects who did not receive the second dose).
- From Dose 1 up to Data lock point, in order to report all SAEs/pIMDs reported at the time of analysis.

* months will be converted in days in order to select the events for the output tables.

Listing of AEs/SAEs leading premature withdrawal from study or to interruption of vaccination will be described in detail.

5.4.2.3. Combined Solicited and Unsolicited Adverse Events

A summary of subjects with all combined solicited (regardless of their duration) and unsolicited adverse events will be provided. Solicited adverse events will be coded by MedDRA as per the following codes:

Solicited symptom	Lower level term code	Corresponding Lower level term decode
Pain	10022086	Injection site pain
Erythema	10015150	Erythema
Swelling	10053425	Swelling at injection site
Fatigue	10016256	Fatigue
Fever	10016558	Fever
Gastrointestinal symptoms	10017944	Gastrointestinal disorder
Headache	10019211	Headache
Myalgia	10028411	Myalgia
Shivering	10040558	Shivering
Arthralgia	10003239	Arthralgia

For clintrial.gov and EudraCT posting purposes, a summary of combined solicited and unsolicited non-serious adverse events will be produced by System Organ Class and preferred terms and according to occurrence of each event.

CONFIDENTIAL208851 (RSV OA=ADJ-002)
Statistical Analysis Plan Amendment 2**5.4.2.4. Clinical Safety Laboratory Investigations**

In case of invalid or missing results or clinically significant grade 3 and above abnormal laboratory findings, a repeat testing may be done to confirm the first result (see Protocol section 7.1.4). For the analysis, the following rules will be applied:

- In general, the first result will be considered, except if this result is missing.
- In case of retesting for a grade 3 at pre-vaccination, the retesting will be considered if the result is < grade 3.
- If result at Visit 1 is missing, the result of the screening will be used as baseline in the analysis.

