10.1.3.7. Counting rules for combining solicited and unsolicited adverse events

For output combining solicited and unsolicited adverse events, all serious adverse events will be considered general events since the administration site flag is not included in the expedited adverse event CRF pages.

Multiple events with the same preferred term which start on the same day are counted as only one occurrence.

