CONFIDENTIAL208851 (RSV OA=ADJ-002)
Statistical Analysis Plan Amendment 2

Note: Templates 45 and 46 will be generated post dose 1 with results at Visit 2 (Day 8) versus baseline at Day 1, and post dose 2 with results at Visit 5 (Day 68) versus baseline at Day 61.

Template Table 46 Summary of hemoglobin change from baseline at 7 days post-dose <1, 2> (Exposed set)

Laboratory parameter	<Each group>		
	N	n	%
Hemoglobin - change from baseline	UNKNOWN		
	GRADE 0		
	GRADE 1		
	GRADE 2		
	GRADE 3		

[figure not shown]
Short group label = long group label

N = number of subjects with at least one available result for the specified laboratory parameter and follow-up period

n/% = number/percentage of subjects reporting at least once the laboratory event when the maximum grading over the follow-up period is considered

Note: This table will be generated post dose 1 with results at Visit 2 (Day 8) and Day 1 as baseline, and post dose 2 with results at Visit 5 (Day 68) and Day 61 as baseline.

Template Figure 10 Boxplot of <each hematology/biochemistry parameter> (Exposed Set)

Note: This graph is given as an example. It will be adapted to display one boxplot per group and per timepoint, all timepoints available (5 TPs: Screening, Days 1, 8, 61, 68). For Part A, one graph will be generated displaying the 4 groups. For Part B, 3 graphs will be generated displaying 4 groups: 3 RSV groups (30/60/120 -Plain, - AS01E or - AS01B) and the Placebo group.

CONFIDENTIAL208851 (RSV OA=ADJ-002)
Statistical Analysis Plan Amendment 2

**Template Table 47 Solicited and unsolicited symptoms classified by MedDRA
Primary System Organ Class and Preferred Term within the 30-day (Days 1-30) post-vaccination period including number of events - SAE excluded <analysis set name>**

			<Each group> N=XXXX			<Each group> N=XXXX		
Primary System Organ Class (CODE)		Preferred Term (CODE)	n*	n	%	n*	n	%
		At least one symptom	XXX	XXX	XX.X	XXX	XXX	XX.X
<each SOC (SOC code)>		At least one PT related to the corresponding SOC <each PT (PT code)>	XXX	XXX	XX.X	XXX	XXX	XX.X
		...	XXX	XXX	XX.X	XXX	XXX	XX.X

Short group label = long group label

At least one symptom = at least one symptom experienced (regardless of the MedDRA Preferred Term)

N = number of subjects included in the considered analysis set in each group

n* = number of events reported

n/% = number/percentage of subjects reporting the symptom at least once

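### Minor: solicited injection-site redness is coded to the unqualified term Erythema, so the combined registry summary shows it without its site

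*SAP*

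**What the plan says.** Three parts of the SAP (Amendment 2) bear on this point.

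- **Definition of the symptom.** Section 5.4.2.1 sets the grading scale for "the maximum intensity of local injection site redness/swelling (in mm"). Redness and swelling share that scale, and grade 1 begins above 20 mm.
- **Coding.** Section 5.4.2.3 says "Solicited adverse events will be coded by MedDRA as per the following codes". In the table that follows, pain (10022086) is decoded as "Injection site pain" and swelling (10053425) as "Swelling at injection site". The erythema row reads "Erythema 10015150 Erythema".
- **Use of the codes.** The same section says that, for posting on the public registries, "a summary of combined solicited and unsolicited non-serious adverse events will be produced by System Organ Class and preferred terms". The matching layout is Template Table 47 in section 12.4, whose title includes "Preferred Term within the 30-day (Days 1-30) post-vaccination period including number of events - SAE excluded". Section 7.1 marks the Day 91 analysis (E1_02) and the final analysis (E1_01) for public posting.

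**The concern.** The coding table treats three local reactions in two different ways. Two keep their site in the coded term and the third loses it, and no reason is given.

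This matters in a table organised only by System Organ Class and preferred term, because there the coded term is the only sign of where an event occurred. A registry reader would see pain and swelling identified as injection-site events, and redness as erythema with no location. If a subject reports erythema elsewhere on the body as an unsolicited event, it lands on the same row. The posted table gives no means of separating the two.

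**Working it through.** The SAP states no figure to reproduce and no arithmetic beyond a count applies, so the check sets the sections side by side.

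1. **Is solicited erythema a local event in this SAP?** Yes. Section 5.4.2.1 grades redness in millimetres at the injection site, on the same scale as swelling.

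2. **How are the three local symptoms coded in section 5.4.2.3?**

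| Solicited local symptom | Code | Site in the decoded term? |
|---|---|---|
| Pain | 10022086 | Yes |
| Swelling | 10053425 | Yes |
| Erythema | 10015150 | No |

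 Two of three carry the site and one of three does not. The difference is visible in the decodes, so no knowledge of the MedDRA hierarchy is needed to see it.

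3. **Which events are affected?** Section 10.1.2.3.1 counts a diary symptom as present once a daily recording reaches grade 1. Every solicited redness above 20 mm is therefore a reported symptom and takes the unqualified term in the combined summary.

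4. **Can the output recover the site?** No. The columns of Template Table 47 are class, preferred term, number of events, number of subjects and percentage. There is no local/general column and no solicited/unsolicited column.

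5. **Can unsolicited erythema reach the same row?** Yes. Section 5.4.1 has each unsolicited verbatim matched to its preferred term. An unsolicited report coded to the same term as solicited redness is tabulated with it.

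6. **Which outputs do not depend on the code?** Template Table 35 lists each solicited local symptom by name, dose and grade. Template Table 33 reports local and general symptoms separately. Section 10.1.3.7 treats all serious events as general because the expedited pages carry no administration-site flag, which indicates that the local/general split rests on that flag and not on the coded term.

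7. **Is the row a slip of the current amendment?** No. It is the same in the first SAP version and in Amendment 1. Section 8, on changes from planned analyses, does not mention it.

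**The case against.** The strongest reply is that little depends on this row. The primary endpoint concerns the occurrence of each solicited event, which is tabulated by named symptom with exact confidence intervals. Template Table 47 is descriptive, has no intervals and supports no comparison. Subjects with redness are still counted in it, in their own row and under the any-symptom line. All of this stands, and it is why the point is minor.

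A reader might infer four stronger things, and the SAP supports none of them as a main harm.

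- **That injection-site reactions are understated across the safety results, or that the primary safety results change.** The by-symptom and local/general tables do not use the code.
- **That general erythema would be inflated in the adjuvanted groups.** The SAP reports no reactogenicity results and does not say that redness depends on adjuvant.
- **That redness moves to a particular System Organ Class.** The SAP does not give the path from lower level term to class.
- **That events are lost through the counting rule in section 10.1.3.7**, "Multiple events with the same preferred term which start on the same day are counted as only one occurrence". This would need one subject to have both solicited redness and an unsolicited event under the same preferred term, starting on the same day. It would lower the event count by one and leave the subject counted once in that row. It is possible but remote.

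It might also be said that mock tables may change without an amendment. Section 12 allows that for editorial and minor changes to the layouts, but the code is set in the body of section 5.4.2.3.

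**Conclusion.** The erythema row is wrong as written and should be corrected, at low priority. The SAP treats solicited erythema as local injection-site redness, gives the other two local symptoms injection-site terms, and offers no reason for treating this one differently.

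The consequence is confined to the combined class and preferred-term summary for registry posting (Template Table 47). There, injection-site redness appears without its site and shares a row with unsolicited erythema elsewhere on the body. Subjects are relabelled in one descriptive table; none is lost from an endpoint.

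The number of subjects involved cannot be derived, because the SAP gives neither a redness rate nor a rate of unsolicited erythema. The statement that Template Table 33 is unaffected rests on reading section 10.1.3.7 to mean that the local/general split comes from the administration-site flag.

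**What to change.** In section 5.4.2.3, change the erythema row to the injection-site erythema lower level term, consistent with the pain and swelling rows. Take the numeric code from the MedDRA version in use; it cannot be verified from the SAP. Apply the new term in Template Table 47 and in the registry outputs for E1_02 and E1_01, so that the two postings agree, and note the change in section 8.

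The cost is one row of the coding table and one line of the mapping program. No data collection, endpoint, model or by-symptom table changes.

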5.4.2.5. Concomitant Medication

Medications will be coded using the GSKDRUG dictionary.

5.5. Analysis of RTI for Part B**5.5.1. Analysis of RTI planned in the protocol**

The analysis will be performed on the ES.

Any RTI episode for which a visit for the assessment of potential RSV-RTI has been performed (with nasal/throat swab sampling) will be considered for the analysis. The assessment of RSV infection will be performed using qRT-PCR on nasal/throat swabs separately for samples collected by the subject and those collected by an appropriately qualified person (i.e., medical or nursing) at the assessment visit.

The proportion of subjects with at least one RSV-associated RTI (with 95 % CI) will be calculated by group.

Descriptive analyses (mean, median, min, max) of viral load assessed by quantitative PCR (RSV-A/B) of RSV-RTI will be performed by study group.

The incidence rate of all-cause RTI (with 95% CI) will be calculated by group. These will also be presented by co-infection identified by multiplex PCR.

5.5.2. Additional considerations

The mean viral load of the RSV positive-RTI samples will also be reported by collection method (at assessment visit or at home) and by collection time (0-2, 3-4, >4 days between RTI onset date of symptoms and collection date).

Information collected at assessment visit will be described for RSV RTI episodes versus Non-RSV RTI episodes, as tested by qRT-PCR on nasal/throat swabs collected at assessment visit. It will include: vital signs, clinical symptoms, self-collected nasal swab result, medically attended visit and SAE related to the episode.

CONFIDENTIAL208851 (RSV OA=ADJ-002)
Statistical Analysis Plan Amendment 2

RTI episodes will be described in detail in a listing. In addition, baseline RSV A Neutralizing antibody titer (GMT and 95% CIs) will be presented graphically by RTI episode status (RSV-RTI vs Non RSV-RTI vs No RTI).

6. ANALYSIS INTERPRETATION

All analyses will be descriptive with the aim to characterize the difference in safety/reactogenicity or immunogenicity between groups.

All comparisons will be exploratory. They should be interpreted with caution considering that there is no adjustment for multiplicity for these comparisons, except for the comparisons of all RSV formulations vs Placebo (Dunnett's adjustment).

7. CONDUCT OF ANALYSES

7.1. Sequence of analyses

The analyses will be performed stepwise:

- **A first analysis** will be performed on all data available and as clean as possible, when data for at least primary and secondary endpoints up to Day 91 are available (except for cell-mediated immune response at pre-Dose 2 [Day 61] in Part A and Part B and the occurrence of RSV RTI in Part B). This will include results from all subjects in Part A and Part B. This analysis will be considered as final for those endpoints. A clinical study report will be written.
At this point, the statistician will be unblinded (i.e., individual subject treatment assignments will be available), but no individual listings will be provided to the study team. Given that summary safety results may unblind some specific subjects, the study will be considered as single-blind from this point onwards, with subjects remaining blinded up to study end (Visit 8, Month 14). The investigators will not be provided with the individual data listings or with the randomization listings until the end of study analysis.
- **A second analysis** will be performed when all safety data up to Month 8 (Visit 7) are available (data as clean as possible). At this time, the following analyses will be performed:
 - The safety analysis of data up to 6 months post-Dose 2.
 - The analysis of all qPCR data available at that time.
 - The analysis of laboratory results that may become available at that time.
- **A third immunogenicity analysis** will be performed when data for at least tertiary immunogenicity endpoints related to persistence (humoral and cell-mediated immunogenicity) up to Month 8 are available, to evaluate the persistence up to 6 months post-Dose 2 in Part B.

CONFIDENTIAL

208851 (RSV OA=ADJ-002)
 Statistical Analysis Plan Amendment 2

- **A fourth analysis** will be performed when data for at least tertiary immunogenicity endpoints related to persistence (humoral and cell-mediated immunogenicity) up to Month 14 (Visit 8) are available for the subjects enrolled in Step 1 of Part B. This analysis will include any additional laboratory results that may become available at that time.

No individual listings will be provided before the final end of study analysis.

- **The final end of study analysis** will be performed when all data for at least primary and secondary endpoints up to study conclusion are available (Month 14). All available tertiary endpoints will also be analysed in this step. Individual listings will only be provided at this stage. An integrated clinical study report containing all available data will be written and made available to the investigators.

If the data for tertiary endpoints become available at a later stage, (an) additional analysis/ analyses will be performed. These data will be documented in annex(es) to the study report and will be made available to the investigators at that time.

Description	Analysis ID	Disclosure Purpose (CTRS=public posting, SR=study report, internal)	Reference for TFL TOC
Final analysis	E1_01	SR, CTRS	See column A in TFL TOC
Analysis up to Day 91	E1_02	SR, CTRS	See column B in TFL TOC
Analysis up to Month 8 (safety and PCR)	E1_03	Internal	See column C in TFL TOC
Analysis up to Month 8 (immuno)	E1_04	Internal	See column D in TFL TOC
Analysis up to Month 14 (Part B Step 1)	E1_05	Internal	See column E in TFL TOC

7.2. Statistical considerations for interim analyses

All confirmatory analyses will be conducted on final data (as clean as possible) and therefore no statistical adjustment for interim analyses is required.

CONFIDENTIAL208851 (RSV OA=ADJ-002)
Statistical Analysis Plan Amendment 2

8. CHANGES FROM PLANNED ANALYSES

Statistical analyses

The fold-increase parameter for CMI (post over pre-vaccination) that will be summarised by group using descriptive statistics (N, geometric mean [GM], min, Q1, median, Q3, max) at each time point during which blood samples are collected for CMI has been adapted as follows:

- ***Fold increase (Post over pre-vaccination)*** of the frequency of RSVPreF3-specific CD4+ T-cells identified as expressing at least 2 marker(s) among IL-2, CD40L, TNF- α , IFN- γ , ***as measured by ICS using PBMCs.***

This analysis was also added for the Memory B cells:

- Fold increase (post over pre-vaccination) of the frequency of RSVPreF3-specific memory B-cells, as measured by ELISpot using PBMCs.

All additional analysis planned compared to protocol are described in the “Additional considerations sections”. The mains ones to be included in the CSR are also described below (changes indicated in bold):

- Demography and baseline characteristics will be summarized ***by country.***
- Vital signs at baseline will be described by group using descriptive statistics.
- Exposure to study vaccine will be tabulated by group and by vaccine
- The ratio of fold increase (post over pre-vaccination) of RSVPreF3 ELISA antibody concentrations over the fold increase (post over pre-vaccination) of RSV neutralizing antibody titers will be reported for RSV-A ***and RSV B.***
- Comparisons with Placebo will be done ***at Day 31*** and Day 91, for both RSV A Neutralizing antibody ***and CD4+ T cells expressing at least 2 markers.***
- Analyses of solicited symptoms were added: incidence of any/local/general solicited AEs, number of days with solicited AEs, analysis on pooled groups according to adjuvant content.
- RTI episodes: analysis of viral load by collection method and collection time was added, as well as the description of signs and symptoms for RSV-RTI vs Non-RSV RTI cases.
- Analysis of hMPV neutralizing antibody titers on all subjects in Part A and on a subset of subjects in Part B.

Sequence of analyses

The wording of the 2nd analysis have been adapted as follows to allow the descriptive analysis of any additional immunogenicity results available for all subjects or for part of them:

CONFIDENTIAL

208851 (RSV OA=ADJ-002)
 Statistical Analysis Plan Amendment 2

- **A second analysis** will be performed when all safety data up to Month 8 (Visit 7) are available (data as clean as possible). At this time, the following analyses will be performed:
 - The safety analysis of data up to 6 months post-Dose 2.
 - The analysis of all qPCR data available at that time.
 - ***The analysis of laboratory results that may become available at that time.***

Sensitivity analysis

An issue in the randomization was identified on 23rd of July, and was identified as Significant Quality Issue (SQI) on the 6th of November 2019.

Randomization were performed in SBIR to create “placeholders”

1. For subjects whose eligibility was not yet confirmed
2. For subjects who were identified and whose ICF was not yet signed
3. For subjects not yet identified

This was not allowed neither based on the protocol, nor by consulting the central team.

As this issue might have an impact on the randomization, a sensitivity analysis will be performed excluding subjects who were randomized after the 23rd of July (randomization date \geq 23JUL2019), for immunogenicity secondary endpoints at the time of first analysis (table template 17 and 22).

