		n	xxx	xx.x	xx.x
		Minimum	xxx		xxx
		Maximum	xxx		xxx
<each interval between study visit>	<interval range>	N	xxx		xxx
		n	xxx	xx.x	xx.x
		Minimum	xxx		xxx
		Maximum	xxx		xxx

Template Table 13 Number of enrolled subjects by country

Characteristics	Categories	<Each group> N = XXX		Total N = XXX
		n	n	n
Country	<each country>			

Short group label = long group label

N = Number of enrolled subjects

n = number of enrolled subjects included in each group or in total for a given country or for all countries

CONFIDENTIAL

208851 (RSV OA=ADJ-002)
 Statistical Analysis Plan Amendment 2

Template Table 14 Number of enrolled subjects by age category

		<each group> N =	Total N =
Characteristics	Categories		
Age category	Adults [18-64 years]	n	n
	Adults [65-84 years]		
	Missing		

Short group label = long group label

N = Number of enrolled subjects

n = number of enrolled subjects included in each group or in total for a given age category or for all age categories

Missing = age at study vaccination unknown

Template Table 15 Minimum and maximum visit dates <analysis set name>

Visit Description	Parameter	<each group>	<each group>	Overall
		Date	Date	Date
< each informed consent>	Minimum	DDMMYYYY	DDMMYYYY	DDMMYYYY
	Maximum	DDMMYYYY	DDMMYYYY	DDMMYYYY
[Randomization]	Minimum	DDMMYYYY	DDMMYYYY	DDMMYYYY
	Maximum	DDMMYYYY	DDMMYYYY	DDMMYYYY
<each visit>	Minimum	DDMMYYYY	DDMMYYYY	DDMMYYYY
	Maximum	DDMMYYYY	DDMMYYYY	DDMMYYYY

Short group label = long group label

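### The sensitivity analysis for the placeholder randomizations excludes by calendar date, not by whether a subject was affected, and repeats none of the planned between-group comparisons

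*SAP*

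**What the plan says.** SAP Amendment 2, section 8, under its sensitivity-analysis heading, gives two dates: "An issue in the randomization was identified on 23rd of July, and was identified as Significant Quality Issue (SQI) on the 6th of November 2019". The nature of the issue is stated: "Randomization were performed in SBIR to create “placeholders". Three kinds are listed: subjects with eligibility still unconfirmed, the group described as "For subjects who were identified and whose ICF was not yet signed", and subjects not identified at all.

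The response follows: "As this issue might have an impact on the randomization, a sensitivity analysis will be performed". Its exclusion is given in words, "excluding subjects who were randomized after the 23rd of July", and then in parentheses as a randomization date on or after 23 July 2019. Its scope is "for immunogenicity secondary endpoints at the time of first analysis (table template 17 and 22". Amendment 1 carries the same text.

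Elsewhere, section 2 says that a subject may be randomized only after eligibility is confirmed, and that Part B minimises on age, center and gender within each step. Section 5.3.1.3 sets out the between-group comparisons in Part B, and section 6 declares every comparison exploratory.

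**The concern.** A check on a randomization problem should do two things: separate the subjects the problem touched from those it did not, and look again at what randomization protects, which is the contrast between groups.

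On the first, a problem identified on a given day had arisen on or before that day. A cut at the identification date therefore does not define the affected subjects. It may leave some in, and it removes unaffected subjects randomized later.

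On the second, the tables chosen describe each group separately. A reader could see whether a group mean moves, but would get no adjusted ratio, interval or test for any contrast.

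At stake is whether the first report can say that the formulation comparisons are robust to the issue. Those comparisons matter for later steps: section 5.3.1.3 lets the test of Day 91 against Day 31 decide the visit used for the adjuvant and antigen-dose comparisons.

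**Working it through.** The SAP gives no figure for this analysis, so there is nothing to reproduce. The check applies the rule to dates and sets the scope against the planned comparisons.

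**1. The date rule (section 8).**

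| Randomization date | Rule in words (after 23 July) | Rule in parentheses (on or after 23 July) |
|---|---|---|
| 22 July 2019 | kept | kept |
| 23 July 2019 | kept | excluded |
| 24 July 2019 | excluded | excluded |

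The two forms disagree for one day. Both keep every earlier randomization.

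**2. Share of affected subjects left in.** Let f be the fraction of placeholder allocations made before the cut; the share retained equals f. The SAP gives no start date, site list or subject list, so f can be anything from 0 (all made on or after 23 July) to 1 (all made before).

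**3. What the repeated tables contain (section 12.3.1).** Template Table 17 gives, by group and time point, the percentage at or above the cut-off and the GMT or GMC with 95% CI. Template Table 22 gives CD4+ T-cell summaries by group, time point and pre-vaccination category, with a Total row. Neither has a between-group ratio or p-value.

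**4. Planned comparisons (sections 5.3.1.3 and 5.3.2.3; section 12.3.2).** There are two assays, RSV-A neutralizing titer and CD4+ T-cell frequency.

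- Template Table 27, against placebo: 9 formulations × 2 assays × 2 visits = 36
- Template Table 28, second dose: 3 pooled groups × 2 assays = 6
- Template Table 29, adjuvant: 3 contrasts × 2 assays × 1 visit = 6
- Template Table 30, antigen dose: 9 pairs × 2 assays × 1 visit = 18

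Total: 36 + 6 + 6 + 18 = 66, before the repeats of the adjuvant contrasts by age category. Template Table 31 holds the model terms. Repeated in the sensitivity analysis: 0 of 66. No safety table is repeated either, although the primary endpoints (section 3.2.1) are all safety endpoints.

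**5. Precision of any reduced set.** Section 2 plans about 70 + 30 = 100 subjects per group in Part B. Interval width scales as 1/√n. The share removed is not given, so these are assumptions:

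- 25% removed: √(100/75) = 1.15, about 15% wider
- 50% removed: √(100/50) = 1.41, about 41% wider
- 75% removed: √(100/25) = 2.00, about 100% wider

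This is loss of precision, not a measure of bias.

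**6. Mix of steps under a date cut.** Step 1 of Part B has about 100 of 1,000 subjects (10%), and its vaccines were reconstituted differently from those of Step 2. If half of Part B were removed and all of those were Step 2 (assumption), the Step 1 share would become 100/500 = 20%. A shift in results could then not be put down to the placeholders alone.

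**The case against.** The strongest reply is that a date cut is the cautious choice. If placeholders fed wrong or missing age and gender into the minimisation, later allocations may also have been disturbed. Dropping only flagged subjects would keep those allocations, whereas dropping everyone from a date onward removes them. This stands, and is why the date cut should be kept as a parallel set.

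Four other points carry weight.

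- A reader might infer that affected subjects are known to remain in the sensitivity set. The document does not show it: the coded rule removes 23 July itself, and all placeholders could date from that day or later.
- A reader might infer that selection bias occurred. Nothing in the SAP says that those who drew placeholders could tell the treatment; randomization was central and the vaccination phase observer-blind.
- A reader might infer from the reference to Template Table 22 that the overall CD4 summary, which is Template Table 21, is lost. The Total row of Template Table 22 supplies it. The list of tables in Amendment 1 numbers the overall table 22, so a stale reference is possible, but little depends on it.
- Elimination codes 900 (invalid consent), 1050 (randomisation failure) and 2010 (eligibility violation) could already remove some affected subjects. Section 4.2 does not tie any of them to the placeholders, and 1050 and 2010 apply to the immunology sets only.

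Template Table 17 is not worthless either: with placebo shown and 95% CIs, a large shift in a group mean would be visible.

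**Conclusion.** The point holds in two parts. The exclusion is set by the identification date, so it cannot be shown to isolate the affected subjects; the share left in is unknown, between 0% and 100%. The scope is clear from the text: none of the 66 comparisons is repeated, although the reason given is a possible effect on the randomization.

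It should be fixed, but it is not a fatal flaw. Section 6 calls all comparisons exploratory, and safety is analysed descriptively on the Exposed Set by the treatment actually given at Dose 1. The documents do not support saying that the trial's results are biased, that the date cut is wrong in itself, or that the planned tables carry no information. The count of 66 assumes that the adjuvant and antigen-dose comparisons are made at one visit, as section 5.3.1.3 describes.

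**What to change.** In section 8:

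1. Add a sensitivity set that excludes every subject whose SBIR randomization precedes signature of the consent form, or precedes confirmation of eligibility where that date is recorded, whatever the calendar date. Consent and randomization dates already feed the table titled "Template Table 15 Minimum and maximum visit dates" (section 12.1). The SAP does not show that an eligibility-confirmation date is held, so this must be checked. If affected subjects cannot be flagged, cut at the first known placeholder date.
2. Keep the 23 July 2019 cut as a parallel set, and say that it addresses possible effects on later minimisation.
3. Repeat Template Tables 27 to 30 on both sets, and preferably the main solicited and unsolicited AE tables.
4. Make the words and the condition agree on 23 July itself, and confirm whether Template Table 21 or 22 is meant.

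The cost is SAP wording, one derived flag, and reruns of existing programs. The downside is wider intervals in the reduced sets. No new data are needed for the consent-based flag; the eligibility-based flag depends on what was recorded.
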